1 STUDY SYNOPSIS

Complete Protocol Title	A multi-centre, non-comparative, prospective post- market clinical follow-up study to obtain survival, clinical and radiographic outcomes data on the Zimmer FitmoreTM Hip Stem.
Protocol Number	09Н06
Short Protocol Title	Fitmore PMCF
Sponsor	Zimmer GmbH
Manufacturer	Zimmer GmbH
Study Device(s)	FitmoreTM Hip Stem
Study Objectives/Endpoints	The objective of this study is to obtain survival, clinical and radiographic outcomes data on the Zimmer FitmoreTM Hip Stem by analysis of standard scoring systems and radiographs.
Indications/Target Population	Patients suffering from severe hip pain and disability requiring total hip arthroplasty.
Inclusion/Exclusion Criteria	 Inclusion Criteria Patients who are capable of understanding the doctor"s explanations, following his instructions and who are able to participate in the follow-up program. Patients who have given written consent to take part in the study by signing the "Patient Consent Form". 18 years minimum. Male and female. Patients suffering from severe hip pain and disability requiring hip surgery or as indicated in the treatment of a fracture. Exclusion Criteria Patients who are unwilling or unable to give consent or to comply with the follow-up program. Pregnancy. Patients who are skeletally immature.
Study Design	A multi-centre, non-comparative, prospective post- marketing study
Clinical Phase	Post-market
Sample Size	500

Length of Study	Collection of preoperative, intra-operative and imme- diate post-operative data; follow-up visits at 6-12 weeks, 1, 2, 3, 5, 7 and 10 years post-operatively. Recruitment period: 24 months.
Materials and Methods	Case report forms will be completed either in-office or hospital at Pre-op, Surgery, Discharge, and the 6 week, 1 year, 2 year, 3 year, 5 year, 7 and 10 year intervals.
Data Collection	Paper/Electronic
Statistical Reporting	Data collected will be summarized and reported to each participating investigator. Statistical analysis will be conducted by Zimmer Biomet or its designee.
Scores/Performance Assessments	Evaluations will be made using the Harris Hip Score, the Oxford Hip Score, the SF-12 Physical and Mental Health summary measures, the EQ-5D (EuroQol) and radiographically.
Standards	 The PMCF is compliant with the below: ISO 14155 Standard for the Clinical Investigation of Medical Devices (part 1 and 2) [1][2].
Study Funding	Funding for this clinical study is made available by Zimmer Biomet to support clinical data collection, IRB/EC review fees and other expenses associated with the conduct and execution of this study protocol as outlined in the fully executed Clinical Trial Agreement.

2 STATISTICAL ANALYSIS PLAN

Statistical Considerations

Data collected in the study will be summarized. Descriptive summaries will be the basis of study reports to participants. Summaries will routinely describe categorical data as counts and percentages, and describe continuous data in the form of means, medians, standard deviations, minima, and maxima.

Summaries of variables such as implant survival, return to function or time to event will generally be described via the Kaplan-Meier method and will be accompanied with the corresponding rates (expressed as percentages). Complication data will be summarized in the form of frequencies and percentages. Summaries may be further generated for strata within the study population, such as males/females, body mass index or primary diagnosis.

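### Return to function is assigned to Kaplan-Meier with no rule for death or stem revision before recovery; if those patients are censored, the reported share recovering will be overstated

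*Combined protocol and SAP*

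**What the plan says.** The SAP's Statistical Considerations name one method for three kinds of variable: "Summaries of variables such as implant survival, return to function or time to event will generally be described via the Kaplan-Meier method". The resulting curves "will be accompanied with the corresponding rates (expressed as percentages"), and the text does not say whether those percentages are one minus Kaplan-Meier or crude shares. It gives no censoring rule, names no competing-risks method, and does not mention death or revision before recovery.

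Return to function is not defined. The Synopsis lists the instruments ("Evaluations will be made using the Harris Hip Score, the Oxford Hip Score, the SF-12 Physical and Mental Health summary measures, the EQ-5D (EuroQol")), but neither section says which of them marks recovery, at what threshold, or from what starting point.

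Three further features bear on the point. Eligibility starts at 18 with no upper age limit and extends to patients "requiring hip surgery or as indicated in the treatment of a fracture". Follow-up is long: "follow-up visits at 6-12 weeks, 1, 2, 3, 5, 7 and 10 years post-operatively". Optional summaries are foreseen for strata "such as males/females, body mass index or primary diagnosis".

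**The concern.** For implant survival, censoring deaths can be defended: the curve then describes how the stem would last in the absence of death. Return to function is different. It is a favourable event, and death before recovery rules it out for good. A censored patient is treated as having the same later chance of recovery as those still followed, so someone who can no longer recover is counted as though part of them will.

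Revision before recovery raises the same issue if the endpoint means recovery with the original stem. If recovery after revision also counts, a revised patient can simply stay in follow-up.

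What is at stake is the meaning of a reported percentage. Readers will take it as the share of patients who regained function. Under censoring it is instead the share who would have done so if nobody died (or was revised) first. The gap grows with the rate of those events, so diagnosis groups with different mortality would be overstated by different amounts.

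**Working it through.** **Plan's own figure.** There is none to reproduce: the documents give no recovery, death or revision rate. The sample size of 500 and the visit schedule come from the Synopsis. Every rate below is an assumption.

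**Calculation on the visit schedule.** Visits are taken at 0.125 (standing for the first visit), 1, 2, 3, 5, 7 and 10 years, with recovery dated to the visit. At each visit let *p* be the chance of recovery among those still unrecovered, and let *q* = 1 − exp(−*c* × interval) be the chance of death or revision since the last visit, at annual rate *c*. *S* is the share still at risk.

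- Kaplan-Meier with these events censored: multiply the curve by (1 − *p*) at each visit; report one minus the result.
- Cumulative incidence: add *S*(1 − *q*)*p* at each visit, then set *S* to *S*(1 − *q*)(1 − *p*).

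Assumed values of *p* at the seven visits:

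- fast: 0.5, 0.8, then 0.2 at each later visit
- medium: 0.2, 0.6, 0.3, 0.2, 0.1, 0.1, 0.1
- slow: 0.1, 0.3, 0.2, 0.1, 0.1, 0.1, 0.1

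One case in full (medium, *c* = 0.03, 1 year):

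- One minus Kaplan-Meier = 1 − 0.8 × 0.4 = 68.0%.
- First visit: *q* = 1 − exp(−0.03 × 0.125) = 0.0037; recovered 0.9963 × 0.2 = 0.1993; still at risk 0.9963 × 0.8 = 0.7970.
- 1 year: *q* = 1 − exp(−0.03 × 0.875) = 0.0259; recovered 0.7970 × 0.9741 × 0.6 = 0.4658.
- Cumulative incidence = 0.1993 + 0.4658 = 66.5%, so the excess is 1.5 points.

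| Recovery | Time | 1 − KM (%) | Cumulative incidence (%) at *c* = 1%, 3%, 5% | Excess (points) |
|---|---|---|---|---|
| Fast | 1 year | 90.0 | 89.5, 88.6, 87.7 | 0.5, 1.4, 2.3 |
| Medium | 1 year | 68.0 | 67.5, 66.5, 65.5 | 0.5, 1.5, 2.5 |
| Slow | 1 year | 37.0 | 36.7, 36.2, 35.6 | 0.3, 0.8, 1.4 |
| Fast | 10 years | 96.7 | 96.0, 94.5, 93.1 | 0.8, 2.2, 3.6 |
| Medium | 10 years | 86.9 | 85.8, 83.6, 81.5 | 1.2, 3.4, 5.4 |
| Slow | 10 years | 66.9 | 65.4, 62.6, 60.0 | 1.5, 4.4, 6.9 |

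Excesses were taken before rounding. With *c* = 0 the two estimates agree.

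**Does the handling rule decide it?** In a simulation of 400,000 patients (medium pattern, *c* = 0.03, no loss to follow-up), the 10-year estimate was 86.8% with these patients censored. It was 83.5% with them kept at risk as not recovered, which is exactly the share who recovered.

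**What makes it larger?**

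- Adding a 5% loss to death or revision before the first visit, on top of 3% a year, gives an excess of 2.6-5.8 points at 1 year and 6.9-7.5 at 10 years.
- A fracture-type stratum can be checked in closed form. Assume 20% never recover and a median of 5 months among the rest, so *r* = ln 2 / (5/12) = 1.664 a year. Assume 15-25% a year die or are revised, so *c* = −ln 0.85 = 0.163 to −ln 0.75 = 0.288. One minus Kaplan-Meier is 0.8(1 − exp(−*rt*)); cumulative incidence is 0.8 × *r*/(*r*+*c*) × (1 − exp(−(*r*+*c*)*t*)). The excess is 3.7-6.3 points at 1 year and 6.1-10.3 at 2 years (at the upper rate, 77.1% against 66.8%).
- The same formula for an elective cohort (10% never recover, median 3 months, *c* = 0.03-0.05) gives 0.7-1.2 points at 1 year and 0.9-1.6 at 2 years.

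**Scale.** The 95% half-width with 500 patients is 1.96 × √(0.8 × 0.2/500) = 3.5 points at a share of 80%, and 1.96 × √(0.9 × 0.1/500) = 2.6 points at 90%.

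**The case against.** The strongest reply is that the plan does not say these patients are censored. A reader might infer from the method's name that they must be, and so that the reported share is too high. The documents do not support that. They are silent on the rule, the word generally leaves the method open, and the accompanying percentages could be crude shares. Keeping these patients at risk as not recovered removes this bias. This part of the reply stands, and the point is therefore conditional. It does not dispose of the matter, because a plan that names Kaplan-Meier and says no more will most likely be carried out with censoring.

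A second reply is that the missing definition is the more basic gap: until return to function has an instrument and threshold, no estimator can be applied, and whether revision competes cannot be settled. That also stands, and the fix begins there.

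Three stronger readings should be resisted.

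- *Early stem failures push the reported recovery rate up.* When death or revision is unrelated to the chance of recovery, as assumed in all the calculations here, one minus Kaplan-Meier does not move as those events become more common. In the elective case it is 84.4% at 1 year at both 3% and 5% a year; only the actual share falls. Failures go uncounted, but nothing here shows that they raise the estimate.
- *Fracture results will be out by 6-10 points.* That needs 15-25% a year dying or being revised. The documents give neither the fracture share nor its mortality, and requiring consent and the ability to attend follow-up would tend to exclude the frailest.
- *Comparisons between strata are invalid.* Stratum summaries are optional, and the study is descriptive with no planned comparison. The remaining risk is that readers set the percentages side by side themselves.

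**Conclusion.** The point holds in conditional form. The direction is certain if death (or competing revision) before recovery is censored; without a stated rule, the documents do not establish that a bias will occur. The assumed 1-5% a year gives an excess that at 1 year is within the sampling error shown for shares of 80-90%. At 10 years under medium recovery (a share in that range), it can exceed that error, at up to 5.4 points. A larger sample would not remove it. These sizes rest on assumed rates, recovery patterns and independence of the two processes. With no hypothesis test or performance threshold in the plan, this is minor to moderate, but it is more than missing detail: for this variable a better-suited estimator than the one named is available at almost no cost.

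**What to change.** Keep Kaplan-Meier for implant survival. For return to function, amend the SAP to:

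1. Define the event: instrument, threshold and time origin. Say whether recovery must be with the original stem.
2. Report the cumulative incidence by the Aalen-Johansen method, with death before recovery as a competing event. Add stem revision before recovery if the endpoint means recovery with the original stem; otherwise keep revised patients in follow-up. Censor only loss to follow-up and end of study.
3. At each reported time show three shares: recovered, died (or revised) without recovery, and not yet recovered. Do this overall and in any diagnosis stratum that is summarised.

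The cost is one or two SAP sentences and a few lines of code. Revision data are already needed for implant survival; the date of death must also be available. Compared with a censored analysis, the reported recovery percentage will be slightly less favourable.

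### Should a competing-risks estimate replace or accompany Kaplan-Meier for 10-year implant survival?

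*Combined protocol and SAP*

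**What the plan says.** The time-to-event plan is one sentence under Statistical Considerations in section 2: "implant survival, return to function or time to event will generally be described via the Kaplan-Meier method and will be accompanied with the corresponding rates", given as percentages. The word for how often this applies is *generally*, so other methods are not excluded, but none is named. The section does not define the implant-survival event, the censoring rules or the handling of deaths. It does not say that any percentage is the proportion of patients revised.

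Two other sentences in that section bear on the point. For complications: "Complication data will be summarized in the form of frequencies and percentages". For subgroups: "Summaries may be further generated for strata within the study population, such as males/females, body mass index or primary diagnosis".

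The Study Synopsis gives the setting. The objective concerns the stem: its survival, and clinical and X-ray outcomes. The design has one group and no comparator, with a sample size of 500. The schedule is "follow-up visits at 6-12 weeks, 1, 2, 3, 5, 7 and 10 years post-operatively". The age criterion is "18 years minimum", with no upper limit, and the indication reads "Patients suffering from severe hip pain and disability requiring hip surgery or as indicated in the treatment of a fracture".

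**The concern.** Over 10 years, some patients in a hip cohort with no age ceiling and with fracture among the indications will die with the stem in place. The usual practice is to censor them at death. One minus Kaplan-Meier is then the revision risk in a hypothetical population in which nobody dies, and it exceeds the share of real patients who are revised. Summaries go to participating investigators, who might read a 10-year figure as that share. A larger sample would not close the gap.

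The plan's other summary could miss in the opposite direction. If revisions are also tabulated as complications, a simple percentage of 500 omits revisions that occur after loss to follow-up. A report could then carry two figures for one event, neither of them the share revised. If subgroup summaries are produced and mortality differs between, say, diagnosis groups, equal Kaplan-Meier figures could go with unequal shares revised.

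**Working it through.** **Inputs.** From the documents: n = 500 and T = 10 years. They give no revision, death or loss rate, so the following are assumptions: net 10-year revision R = 5% (2% and 10% as alternatives), 10-year mortality D from 10% to 50%, and independent hazards. The 500 comes without a derivation, so there is no planning figure to reproduce.

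**Constant hazards.** Let r = −ln(1−R)/10 and d = −ln(1−D)/10. With deaths censored, one minus Kaplan-Meier estimates 1 − exp(−10r) = R. The share actually revised is

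r/(r+d) × [1 − exp(−10(r+d))].

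For R = 5% and D = 20%: r = 0.005129, d = 0.022314, r/(r+d) = 0.1869, and 1 − 0.95 × 0.80 = 0.24. The product is 0.0449.

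**Early-loaded revision.** Half of the cumulative revision hazard (0.051293/2 = 0.025647) falls in year 1 and the rest is even over years 1 to 10 (b = 0.025647/9 = 0.002850 per year). With a = 0.025647, the share revised is

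a/(a+d) × [1 − exp(−(a+d))] + exp(−(a+d)) × b/(b+d) × [1 − exp(−9(b+d))].

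At D = 20% this is 0.0250 + 0.0219 = 0.0469.

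**Results for R = 5%.**

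| 10-year mortality | Share revised, constant | Gap (points) | Share revised, early-loaded | Gap (points) |
|---|---|---|---|---|
| 10% | 4.75% | 0.25 | 4.85% | 0.15 |
| 20% | 4.49% | 0.51 | 4.69% | 0.31 |
| 30% | 4.21% | 0.79 | 4.53% | 0.47 |
| 50% | 3.62% | 1.38 | 4.16% | 0.84 |

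A simulation of 4,000 cohorts of 500 at R = 5%, D = 20% and constant hazards gave a mean Kaplan-Meier complement of 5.02% and a mean observed share of 4.50%, in line with the formula. Per 500 patients that is about 25 against 22 revisions.

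**Sampling error.** With complete follow-up the binomial standard error is √(0.05 × 0.95/500) = 0.97 points. With 20% deaths and 20% loss (c = 0.022314, k = r+d+c = 0.049758), the Greenwood form is 0.95 × √{r/(500k) × [exp(10k) − 1]} = 0.95 × √(0.005129 × 0.6447/(500 × 0.049758)) = 1.10 points. The gap at 20% mortality is 0.51/1.10 = 0.47 of a standard error with constant hazards, or 0.31/1.10 = 0.28 with early-loaded revision.

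**Sensitivity to R, constant hazards, D = 20%.** At R = 2% the gap is 0.21 points. At R = 10% it is 1.02 points, against a standard error of about 1.42. With R = 10% and D = 40% the gap is 2.13 points and exceeds the standard error of about 1.54.

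**Simple percentage.** With 20% deaths and 20% loss it is r/k × [1 − exp(−10k)] = 0.1031 × (1 − 0.95 × 0.80 × 0.80) = 0.1031 × 0.392 = 4.04%, against a true share of 4.49%. This matters only if revisions are counted among complications, which the plan does not say.

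**The case for a change.** The best case for a change is that the plan promises percentages without saying what they are percentages of, and that neither planned summary estimates the share of patients revised. Clinicians may want that share. The addition would be cheap: a few sentences, one curve and one table. It does need dated deaths kept apart from loss to follow-up, and after year 3 the visits are 2, 2 and 3 years apart, so dates not collected at the time may be hard to recover. The gap can also be material. At 50% mortality with constant hazards it is 1.38 points, above the Greenwood standard error of about 1.17 for that mortality.

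The arithmetic stands, and so does the observation that the section is silent on deaths. What does not follow is that the planned figure is wrong. Net implant survival and the share of patients revised are two different quantities. The distance between them becomes bias only if one is presented as the other, and nothing in the documents does that. The high-mortality case has little support either: eligible patients must be able to take part in the follow-up programme, and those who cannot comply are excluded. The subgroup point depends on summaries that are optional and on mortality differing between groups.

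**Conclusion.** No change is needed. The plan sets out to describe how long the stem survives, and Kaplan-Meier with deaths censored does so, on the condition that death and loss to follow-up are independent of revision risk. The study is descriptive, with one group and no hypothesis or threshold that a gap of this size could overturn.

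At an assumed 5% net revision and 20% mortality, the complement exceeds the share revised by about 0.3 to 0.5 points, under half of a 1.10-point standard error. The gap passes one standard error only with much higher mortality or about twice the assumed revision risk. Even there the Kaplan-Meier figure remains a correct estimate of what the plan names.

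The event definition, the censoring of deaths and a label such as net implant survival are missing details that an analyst would supply as a matter of course. A cumulative incidence with death as a competing event (Aalen-Johansen) would be needed only if a report were to state the proportion of patients revised, which this plan does not promise.

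### Does the SAP need to prescribe confidence intervals, numbers at risk and time points for its Kaplan-Meier estimates?

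*Combined protocol and SAP*

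**What the plan says.** The analysis plan is section 2, Statistical Analysis Plan, under Statistical Considerations, and it is short. On time-to-event outcomes it says: "Summaries of variables such as implant survival, return to function or time to event will generally be described via the Kaplan-Meier method", and that these "will be accompanied with the corresponding rates (expressed as percentages"). For continuous data it is more specific and will "describe continuous data in the form of means, medians, standard deviations, minima, and maxima". On use of the results: "Descriptive summaries will be the basis of study reports to participants". Subgroup summaries are optional: "Summaries may be further generated for strata within the study population, such as males/females, body mass index or primary diagnosis".

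The synopsis (section 1) supplies the context. The design is "A multi-centre, non-comparative, prospective", the sample size is 500, and the Length of Study row gives "follow-up visits at 6-12 weeks, 1, 2, 3, 5, 7 and 10 years post-operatively" and "Recruitment period: 24 months". The objective lists survival before clinical and radiographic outcomes. Neither section mentions a confidence level, a standard error or a number at risk, and neither ties the Kaplan-Meier percentages to the visit years. No redaction mark appears in the SAP text.

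**The concern.** A Kaplan-Meier percentage needs a time attached to it, and in a single-arm study it also needs a measure of precision. There is no control group and no hypothesis test to give context, so the estimate and its uncertainty are the whole finding. The SAP names a standard deviation for continuous variables but no comparable measure for survival. Read literally, a report could print one 10-year survival figure, show neither its interval nor how many patients were still under observation, and comply with the plan.

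Two things make that uncomfortable. The planned 500 does not tell a reader how many remain at risk late in follow-up, because that depends on death, loss and the report date, and the documents give none of these. And if small strata are reported, one with no events would print 100% with nothing to show how little that may mean.

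**Working it through.** **Is there a plan figure to reproduce?** No. The sample size of 500 comes with no expected survival, precision target, dropout rate, alpha or power. What follows only illustrates how much a bare percentage would leave out.

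**Inputs from the documents:** n = 500; recruitment over 24 months; visits up to 10 years.

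**Assumptions:** constant event and censoring hazards; 10-year survival S of 95% (range 90% to 98%); death or loss by 10 years of 40% (range 0% to 60%); 95% limits on the log-log scale.

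**Formulas.** Event hazard l = -ln(S)/10 and censoring hazard c = -ln(1 - loss)/10. The variance of the log survival estimate at time t is

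v = (l/n) × [exp((l + c)t) - 1]/(l + c).

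The limits are S(t) raised to the power exp(±1.96·√v/|ln S(t)|). The number at risk is n·exp(-(l + c)t).

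**Base case at 10 years**
- l = 0.005129, c = 0.051083, sum 0.056212.
- exp(0.56212) = 1/(0.95 × 0.60) = 1.7544.
- v = (0.005129/500) × 0.7544/0.056212 = 0.0001377, so √v = 0.01173.
- √v/|ln 0.95| = 0.01173/0.05129 = 0.2288, and exp(±1.96 × 0.2288) = 1.566 and 0.639.
- Limits: 0.95^1.566 = 92.3% and 0.95^0.639 = 96.8%. Failure is 3.2% to 7.7%, a ratio of 2.4.
- At risk: 500 × 0.95 × 0.60 = 285, if everyone remaining is followed past 10 years.

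**Over the assumed ranges at 10 years**

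| Survival | Loss | 95% interval | Ratio of failure limits |
|---|---|---|---|
| 90% | 0% | 87.0–92.3% | 1.69 |
| 90% | 60% | 86.0–92.9% | 1.96 |
| 95% | 0% | 92.7–96.6% | 2.15 |
| 95% | 60% | 91.9–96.9% | 2.66 |
| 98% | 0% | 96.3–98.9% | 3.41 |
| 98% | 60% | 95.6–99.1% | 4.80 |

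The ratio looks largest where failure is rarest. On the survival scale the base-case interval is 96.8 - 92.3 = 4.5 points wide.

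**Number at risk and report date.** With uniform accrual over two years, a report T years after first enrolment (T between 10 and 12) multiplies the 285 by (T - 10)/2. That gives 285 × 0.25 = 71 at 10.5 years and 285 × 0.05 = 14 at 10.1 years. In the second case the interval widens only to 91.5–97.1%, since most of the information comes from earlier follow-up.

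**Does the omission alter anything else?** The point estimates are the same with or without intervals. The intervals and numbers at risk come from the event and censoring times already needed for the curve. The documents state no test, margin or decision rule that would use them.

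**The case for a change.** The strongest case for a change is that the plan lets a designee do the analysis, requires no measure of precision for the study's first-named outcome, and leaves the time points open, so they could be chosen once the curve has been seen. The remedy would cost a few sentences and no data.

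Part of this stands. The three items are absent from the text, and a percentage alone would hide an interval of several points. But the consequence is small. A Kaplan-Meier description covers the whole of follow-up, so naming particular years selects nothing that the curve does not already show, and the visit years in the synopsis are the natural places to read it. Pointwise intervals and numbers at risk are what an analyst running Kaplan-Meier would ordinarily report, and the plan does not forbid them. The argument from small strata carries little weight, because those summaries are optional and their sizes are unknown.

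Nor is a prescriptive rule as simple as it looks. Limiting the estimates to years 1, 2, 3, 5, 7 and 10 would give return to function no time point before one year. The log-log interval is undefined when the estimate reaches 0, as it could for return to function, or when it stays at 100%. The text would also have to say whether a visit year means the anniversary or the visit itself: if last visits fall evenly either side of 10 years, the number at risk at exactly 10 years halves from 285 to about 143. An analyst can settle these points when the outputs are specified.

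**Conclusion.** The observation is accurate, but it does not call for a change to the plan. It concerns reporting detail in an openly descriptive, single-arm study. No stated rule yields a wrong result, no estimate would differ, and nothing about enrolment or data collection depends on it. The uncertainty that a bare percentage would conceal is real: 92.3% to 96.8% at 10 years in the base case, with the upper failure limit 1.7 to 4.8 times the lower across the ranges tried. Those figures rest on assumed survival, loss and constant hazards; only the 500 patients, the 24-month recruitment and the visit schedule come from the documents. Competent analysis of the same data would show that uncertainty without an amendment. Giving intervals and numbers at risk at the visit years is sensible practice for the report and can be left to the analyst.

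### Complications over 10 years are to be given as percentages with no denominator or time point; for late complications this can shift the reported risk modestly if patients are lost or die (minor)

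*Combined protocol and SAP*

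**What the plan says.** Complications have one sentence in section 2 (Statistical Analysis Plan, Statistical Considerations): "Complication data will be summarized in the form of frequencies and percentages". The general rule for categorical variables in the same section, "Summaries will routinely describe categorical data as counts and percentages", also names no denominator. Neither sentence gives a time point or says whether patients or events are counted.

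The sentence just before the one on complications covers time-dependent outcomes: "Summaries of variables such as implant survival, return to function or time to event will generally be described via the Kaplan-Meier method". Complications are not named there.

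Section 1 (Study Synopsis) plans 500 patients, with "follow-up visits at 6-12 weeks, 1, 2, 3, 5, 7 and 10 years post-operatively. Recruitment period: 24 months". Neither section states an expected loss to follow-up or how loss and death are to be handled.

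On reporting, section 2 says "Descriptive summaries will be the basis of study reports to participants".

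**The concern.** Over 10 years some patients may be lost or die before a late complication could be seen. A percentage of late complications can be read as a risk at a stated time only if the plan fixes who is in the denominator and by when. An analyst could follow the present sentence exactly and still choose among several percentages:

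- Dividing by everyone enrolled counts lost patients as free of complications after they leave, so it understates the risk.
- Dividing by patients with an event plus those who completed follow-up without one drops the event-free time of lost patients, so it overstates the risk.
- Using only patients followed to the visit, in both numerator and denominator, is unbiased when loss is independent. It ignores events seen in patients lost later and, if patients die, describes survivors only.

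The gap is narrow. Complications during surgery or before discharge have close to a full denominator. Complications that lead to stem revision are presumably captured by the implant survival curve, although the text does not define that outcome. That leaves late complications without revision. Since study reports are built on descriptive summaries, the chosen percentage is what readers will see.

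**Working it through.** The plan has no complication figure to reproduce, so this is an illustration.

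**Inputs from the documents:** n = 500; T = 10 years (section 1).

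**Assumed:** true 10-year risk of a first late complication 10%; constant hazards; loss L by 10 years of 10%, 20%, 30% or 40%, independent of complication risk; at first, no deaths.

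**Formulas**

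- Complication hazard: λ = −ln(0.90)/10 = 0.01054 per year.
- Loss hazard: δ = −ln(1 − L)/10. Total: h = λ + δ.
- Proportion with an observed event: E = (λ/h)(1 − e^(−10h)).
- Proportion completing 10 years without an event: C = e^(−10h) = 0.90(1 − L).
- All-enrolled percentage = E. Event-or-completer percentage = E/(E + C).

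**Example, L = 20%:** δ = 0.02231 and h = 0.03285. E = 0.3207 × (1 − 0.72) = 0.0898, or 44.9 expected events in 500. C = 0.72. The all-enrolled figure is 9.0%, and event-or-completer is 0.0898/0.8098 = 11.1%.

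| Loss by 10 years | Expected observed events | All enrolled | Event-or-completer | Followed to the 10-year visit |
|---|---|---|---|---|
| 10% | 47.5 | 9.5% | 10.5% | 10.0% |
| 20% | 44.9 | 9.0% | 11.1% | 10.0% |
| 30% | 42.2 | 8.4% | 11.8% | 10.0% |
| 40% | 39.3 | 7.9% | 12.7% | 10.0% |

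The bias of the first two percentages is 0.5 to 1.1 points at 10-20% loss and 2.1 to 2.7 points at 40% loss. For scale, the 95% sampling half-width for 10% of 500 is 1.96 × √(0.09/500) = 2.6 points. With no loss all columns equal 10.0%.

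**What the followed-to-visit percentage gives up.** It uses 500 × 0.10 × (1 − L) = 45, 40, 35 and 30 events, so it discards 5%, 11%, 17% and 24% of those observed. Its half-width, 1.96 × √(0.09/(500(1 − L))), is 2.8, 2.9, 3.1 and 3.4 points. A cumulative incidence, by the asymptotic Greenwood formula 1.96 × √(0.81(λ/h)(e^(10h) − 1)/500), has 2.7, 2.8, 2.9 and 3.0. The gain in precision is therefore small, at most about 0.4 points.

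**Adding deaths.** Let D be the proportion dead by 10 years from a death hazard μ = −ln(1 − D)/10. Re-solve λ so that the true cumulative incidence, (λ/(λ + μ))(1 − e^(−10(λ + μ))), stays at 10%. This gives λ = 0.01112 for D = 10% and 0.01219 for D = 25%. Among those alive at 10 years, the proportion with a complication is 1 − e^(−10λ) = 10.5% and 11.5%. With 30% loss and 25% deaths together, the all-enrolled percentage is 8.5% and the followed-to-visit percentage 11.5%. In a simulation of 2,000,000 patients with those rates, the cumulative incidence with death as a competing event (Aalen-Johansen) recovered 10.0%.

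**The case against.** The strongest reply is that this is an unspecified detail in a purely descriptive, non-comparative study. Complications are not named in the synopsis objective, there is no decision threshold, and implant survival, the time-dependent outcome the study does name, already has Kaplan-Meier. Every rate above is assumed, and at 10-20% loss the bias is less than half the sampling half-width. A one-sentence rule giving the percentage among patients followed to a stated visit, with both counts shown, would be unbiased under independent loss and would almost match cumulative incidence in precision. When patients die, that percentage describes survivors, which is a different target and not simply an error. Most of this stands, and it is why the point is minor.

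A reader might infer something stronger: that the plan excludes Kaplan-Meier for complications, or that its late-complication results will be materially wrong. The text supports neither. The Kaplan-Meier sentence is worded as an illustrative list with a general time-to-event category, so it permits the method for time to first complication. Any bias needs loss or death that the documents do not quantify.

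The objection does not remove the gap itself. Permission is not a commitment, the complication sentence states a method of its own, and that method can yield different figures from the same data.

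**Conclusion.** The point holds as a minor one. The plan leaves the denominator and time point of complication percentages open while assigning a censoring-aware method to other time-dependent outcomes over the same 10 years. For late complications without revision, an all-enrolled percentage understates the risk if patients are lost, and an event-or-completer percentage overstates it. The illustrated spread between them is 1.0 point at 10% loss (10.5 − 9.5) and 4.8 points at 40% loss (12.7 − 7.9). These sizes rest on an assumed 10% risk, constant hazards and independent loss. The omission is certain; its practical effect is not known. It bears on how a reported estimate is read and changes no conclusion or named endpoint.

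**What to change.** Keep the present sentence for early events and add a rule for later ones. Suggested wording:

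> Counts of complications will be tabulated. Intra-operative and pre-discharge complications will also be given as a percentage of all patients operated on. For later complications, at least for any complication and for the main types, the cumulative incidence of first occurrence will be reported at the planned follow-up visits, with the number at risk and a 95% confidence interval. Patients will be censored at last follow-up and death will be a competing event. Timing will be taken from the onset date or, if that is not collected, from the visit interval in which the complication was first recorded.

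If timing cannot be recovered, the minimum is a percentage among patients followed to a stated visit, with numerator and denominator taken from the same patients and both shown. That costs one sentence, discards some events and describes survivors only.

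The main version costs a change of wording and a little more analysis. It uses visits already scheduled. Section 1 has case report forms completed at each of them, but the documents do not show what the forms contain, so whether they record timing must be checked. The estimate assumes that loss is unrelated to complication risk, which should be stated with the results. Late rates may look slightly less favourable than an all-enrolled percentage.
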